| Précis: | Patients undergoing a bone marrow biopsy aspiration (BMBA) will trial possible interventions to decrease their distress and pain , as suggested by a previous patient survey conducted with this population. The study will assess both pre-intervention and post-intervention distress scores and a post-intervention pain score. Patient satisfaction will also be assessed to determine overall patient experience. Each intervention will be compared to a control group to validate if one or both interventions are valuable to offer to patients in the future. |
| Objectives: | 
Primary: Trial VR and environmental interventions to determine if either result in a reduction in patient distress during BMBA.
 
Secondary: Determine if either intervention results in decreased pain or improved satisfaction scores.
 |
| Population: | 
Young adult to geriatric patients with hematologic malignancies of varying health statuses and demographic groups
 
Most patients have hematological cancers, including leukemia, lymphoma, and multiple myeloma.
 |
| Phase: | N/A |
| Number of Sites: | TJU |
| Description of Intervention: | 
Two interventions will be trialed. The first intervention is virtual reality (VR) guided mediation. Patients will be provided with wireless VR headsets that contain a guided meditation application. The application allows users to select their preferred music, visual setting, and a topic for meditation.
 
The second intervention is environmental changes. A nature themed wall mural decal will be installed in the BMBA room and the in-room computer will play music from Pandora. A selection of suggested stations will be provided, with the option for outside selections.
 |
| Study Duration: | 10 months |

| | |
|---|--|
| Participant Participation Duration: | Approximately 45 minutes, the duration of a normal BMBA visit, including procedure |
| Estimated Time to Complete Enrollment: | 6 months |

Schematic of Study Design:

1 Introduction

1.1 Background Information

Bone marrow biopsies are frequent occurrences for hematological cancer patients. These procedures are a source of anxiety for many patients. Current literature suggests a wide variety of changes that can be employed to reduce stress and improve patient experience, including: room décor changes^{1, 2, 3, 4} some including nature inspired imagery,^{3, 5, 6} music for relaxation during procedure,^{7, 8, 9, 10} guided meditation,^{11, 12} virtual reality (VR) distraction therapy,^{13, 14, 15, 16, 17, 18} etc. These changes have the potential to decrease patient stress both prior to procedures^{9, 19} and during them.¹⁶

In a human-centered design survey conducted by this team in December 2019, patients were asked about their pain and anxiety relating to BMBA procedures, as well as their thoughts on possible interventions. A large majority (72%, n=16) of patients believed that the addition of music to their treatment would improve their experience. Other options were also considered including virtual reality (26%, n=5) and guided meditation

(30%, n=6). Though fewer patients expressed interest in these interventions, only 8% (n=2) had previously experienced guided meditation and none of the patients surveyed had any experience with VR. For this reason investigators will trial two interventions with patients to determine if one or both are effective at improving the patient experience. The overall goal of the study is to identify an intervention—or both interventions—as a potential offering for patients during BMBA procedures to improve their overall experience.

1.2 Rationale for the Proposed Study

Human-centered design puts “the user at the core of the design process” and allows spaces to be adapted to actual desired needs rather than perceived needs.^{20,21} The interventions being trialed were selected with the target patient population as part of the conversation.

Intervention 1 provides patients with a guided meditation experience through a VR headset. Existing literature shows that guided imagery increases patient comfort and that meditation can substantially improve “psychological function, mental health, and [quality of life]” for cancer patients.²² VR has also been shown to be an “effective distraction intervention for managing pain and anxiety among breast cancer patients,”²³ during lumbar punctures¹³ and for patients with chronic pain.^{15, 18} Participants will be introduced to the Oculus Go VR headset while waiting in the procedure room prior to their procedure. They will use the headset for approximately 10 minutes, or until their provider arrives for their procedure. The provider will prepare the patient for their BMBA procedure, and then allow them to continue using their VR headset and chosen guided meditation during the procedure, for approximately 20 minutes. Oculus guidelines suggest new users take breaks every 30 minutes or as needed while adjusting to the technology.²⁴ Participant usage should fit within this suggested timeframe.

Intervention 2 provides patients with changes to their procedure room environment. Natural environments have a positive influence on human perceptions of stress²⁵ and allow for greater recovery from mental fatigue.²⁶ Furthermore, natural interior design, including soundscape,² can have restorative properties for patients.^{1, 4} In particular, music therapy improves “anxiety and depression symptoms presented by patients with cancer,”²⁷ has been associated with lower pain scores for palliative care patients,²⁸ and been used for anti-anxiety interventions for outpatient procedures,¹⁰ including BMBA.⁸ For this intervention, participants will be able to select their preferred type of music for the duration of their time in the procedure room, including while waiting before their procedure. They will be provided with a list of suggested music types, based on the previous patient survey’s results, but will also have the option to select outside the list based on their preference.

Our hypothesis is that patients undergoing bone marrow biopsy and aspiration (BMBA) who receive distraction techniques (room décor, music, and virtual reality) will have lower levels of distress and pain than patients who receive only the standard of practice care. Additionally, these patients will have higher levels of satisfaction with their overall experience. This study aims to evaluate pre-procedure and post-procedure distress and

pain scores, and post-procedure satisfaction ratings to determine if one or both of the selected interventions are valuable to employ in-clinic for the entire patient population.

1.3 Potential Risks and Benefits

1.3.1 Potential Risks

Potential risks vary based on intervention arm.

Intervention 1: Virtual reality may cause symptoms associated with motion sickness, including nausea, dizziness, disorientation, and vertigo.²⁹ Mild eyestrain or headaches may also occur.

Intervention 2: There are no known risks associated with music therapy or décor changes.

Participants in all study arms will undergo a BMBA procedure as part of their standard care. Potential risks of bone marrow biopsies are bruising and pain at the biopsy site, discomfort at the site during or post-procedure, prolonged bleeding, and infection.

1.3.2 Benefits

Potential benefits include improved patient satisfaction, reduction of acute pain perception, decreased distress around BMBA, and overall improvement in patient experience.

2 Study Objectives

2.1 Objectives

2.1.1 Primary

To assess patient distress scores related to BMBA procedures.

The primary outcome will be reported on a scale of 0-10, based on the National Comprehensive Cancer Network (NCCN) Distress Thermometer. This scale is standardly used with oncology patients to determine their distress levels—distress refers to “an unpleasant experience of a mental, physical, social, or spiritual nature. It can affect the way you think, feel, or act. Distress may make it harder to cope with having cancer, its symptoms, or its treatment.”³⁰

2.1.2 Secondary

To assess patient pain scores related to their BMBA procedure. This will be measured through the 0-10 Numeric Pain Intensity Scale

To assess patient satisfaction with their procedure. This will be assessed through a patient satisfaction survey including Likert-type questions.

2.2 Endpoints/Outcome Measures

Primary outcomes will be assessed via the patient questionnaires. All endpoints are measured pre- and post-procedure at Visit 1.

2.2.1 Primary

The primary endpoint of patients' distress levels towards BMBA procedures are the responses to Question 13 and 16 of the survey (Appendix B).

2.2.2 Secondary

The secondary endpoint of patients' pain scores during BMBA procedures are the responses to Question 12 and 17 of the post-procedure survey.

The secondary endpoint of patients' satisfaction levels towards their BMBA procedures is the response to Questions 18 of the post-procedure survey.

3 Study Design

3.1 Characteristics

Trial of interventions to improve patient experience during BMBA procedures at outpatient oncology office.

3.2 Number of Participants

60 total patients will be enrolled in the study. For Phase I, 15 patients will enroll in Intervention 1 and 15 patients will enroll in the control arm. For Phase II, 15 patients will enroll in Intervention 2 and 15 patients will enroll in the control arm.

3.3 Duration of Therapy

Approximately 20-30 minutes of a 45-minute visit. No follow-up visit will occur.

3.4 Treatment Assignment Procedures

3.4.1 Randomization Procedures

We will adopt a permuted block randomization schedule for both Phase I and II. Study staff will utilize a sealed envelope system provided by the Biostatistics department.

3.5 Study Timeline

Patients will be enrolled on a rolling basis as they are scheduled for their BMBA procedures. We anticipate enrolling 2-3 patients per week, resulting in a 6-month timeline to achieve 60 participants. Both primary and study completion dates will conclude at the end of the enrollment period.

4 Study Enrollment and Withdrawal

Pregnant women are not commonly a part of the BMBA patient population, but there is no reason to exclude their participation so pregnancy will not be included in the exclusion criteria.

4.1 Eligibility Criteria

4.1.1 Inclusion Criteria

Individuals must meet all of the following inclusion criteria in order to be eligible to participate in the study:

- Provide signed and dated informed consent form
- Willing to comply with all study procedures
- Over 18 years of age
- Prior history of at least 1 (one) BMBA at Jefferson outpatient oncology office within the past 2 (two) years
- Visiting the Jefferson outpatient oncology office for a BMBA procedure during the study duration

4.1.2 Exclusion Criteria

An individual who meets any of the following criteria will be excluded from participation in this study:

- Inability to read questions in English
- Inability to answer questions autonomously
- History of vertigo
- Legal blindness in both eyes
- Severe or profound hearing loss, or deafness

4.2 Gender/Minority/Pediatric Inclusion for Research

Pediatric patients are not included in this study as they are not treated at the outpatient medical oncology office at [name] where it is being conducted. All adult patients, regardless of gender or minority will be included.

4.3 Strategies for Recruitment and Retention

Participants will be recruited from patients already attending the outpatient medical oncology office at [name] for BMBA procedures. Study staff will review the BMBA schedule a week prior to procedures and call patients who fit the inclusion criteria to

inform them about the study. This will include a discussion of the goals of the study, expectations for participation, and a general overview of the consent process.

Participation is for a one-time session and retention will not be necessary.

4.4 Participant Withdrawal

4.4.1 Reasons for Withdrawal

Participants are free to withdraw from participation in the study at any time upon request.

An investigator may terminate a study participant's participation in the study if:

- Any clinical adverse event (AE), laboratory abnormality, or other medical condition or situation occurs such that continued participation in the study would not be in the best interest of the participant.
- The participant meets an exclusion criterion (either newly developed or not previously recognized) that precludes further study participation.

4.4.2 Handling of Participant Withdrawals and Participant Discontinuation of Study Intervention

Any participant who experiences an AE and discontinues participation will be asked to provide details about their experience. They may also be asked to complete the post-procedure survey, if deemed appropriate by study staff.

4.5 Premature Termination or Suspension of Study

This study may be suspended or prematurely terminated if there is sufficient reasonable cause. Written notification, documenting the reason for study suspension or termination, will be provided by the suspending or terminating party to the investigators, funding agency and regulatory authorities. If the study is prematurely terminated or suspended, the principal investigator will promptly inform the IRB and will provide the reason(s) for the termination or suspension.

Circumstances that may warrant termination include, but are not limited to:

- Determination of unexpected, significant, or unacceptable risk to participants.
- Insufficient adherence to protocol requirements.
- Data that is not sufficiently complete and/or evaluable.
- Determination of futility.

5 Study Intervention

5.1 Study Product

The Phase I intervention is virtual reality (VR) guided mediation. Patients will be provided with a wireless VR headset that contains a guided meditation application. The application allows users to select their preferred music, visual setting, and a topic for meditation. Patients who are enrolled to this study group will receive instructions on how to use the VR device prior to the procedure.

The Phase II intervention involves environmental changes. A nature-themed wall mural decal will be installed in the BMBA procedure room, and the in-room computer will play music from Pandora. A selection of suggested stations will be provided, with the option for outside selections if desired.

6 Study Schedule

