6.2 Enrollment/Baseline

Enrollment/Baseline (Visit 1, Day 1)

- Obtain and document consent from participant on study consent form. Consent interview will be conducted in a private room separate from the procedure room.
- Verify inclusion/exclusion criteria.
- Randomize patient to Control or Intervention arm via sealed envelope.
- Administer pre-procedure survey which includes:
 - Demographic information and focused medical history.
 - Assessment of current distress level (0-10 scale).

- Escort patient to procedure room.
- Obtain baseline vital signs: heart rate, blood pressure, respiratory rate.
- If randomized to an intervention group, provide intervention-specific instructions.
 - For Intervention 1, patients will be instructed on how to put on and use the VR headset and how to select their preferred guided meditation.
 - For Intervention 2, patients will be provided with Pandora music station options or allowed to select their own option.

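### Phase II has no written step that keeps control patients from seeing the wall mural, so as written it compares music against no music with the mural in both arms

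*Combined protocol and SAP*

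**What the plan says.** Intervention 2 has two parts, a wall decal and music chosen by the patient. The decal belongs to the room. Section 5.1 states "A nature-themed wall mural decal will be installed in the BMBA procedure room", and the synopsis (Description of Intervention) says the same: "A nature themed wall mural decal will be installed in the BMBA room".

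Section 3.2 gives Phase II its own controls: "For Phase II, 15 patients will enroll in Intervention 2 and 15 patients will enroll in the control arm". Section 3.4.1 adds: "We will adopt a permuted block randomization schedule for both Phase I and II".

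Section 6.2 sets the order on the procedure day, after consent and the eligibility check:

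1. "Randomize patient to Control or Intervention arm via sealed envelope"
2. "Administer pre-procedure survey which includes" the current distress score
3. "Escort patient to procedure room"
4. Intervention-specific instructions. For Intervention 2 the only one is the choice of music.

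The hypothesis in sections 1.2 and 11.1 names room décor among the techniques under test. It sets the comparator as "patients who receive only the standard of practice care". Section 11.2 compares the post-minus-pre distress difference between Intervention 2 and Control within Phase II by a two-sample t-test.

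**The concern.** A mural fixed to a wall cannot be given to one patient and withheld from the next unless something is done to the room or the patient uses another room. Permuted blocks interleave the two arms over time, so no single installation date separates them. The plan describes no cover, removal step or arm-specific room.

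If controls see the mural, it is common to both arms and drops out of the comparison. What remains is a valid randomised estimate of adding music in a room that already has the mural. That is a different question from whether the décor-and-music package improves on usual care, and the study is meant to decide whether the package is worth offering. A null Phase II result could not then be read as failure of the package, because part of it would have been given to the controls.

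The primary endpoint is exposed. Baseline distress (Q13) is recorded before the patient enters the procedure room and follow-up distress (Q16) after the procedure, so any mural effect in controls falls inside their pre-to-post change. Among the secondary endpoints, Q18 asks all patients to rate the room décor, and both arms would be rating the same décor.

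**Working it through.** **The plan's own figure.** Section 11.3 states 82.8% power for 15 per arm, effect size 1.1, two-sided 5%, equal-variance t-test. With 28 degrees of freedom and noncentrality 1.1 × √(15/2) = 3.01, the exact noncentral-t calculation gives 82.8%. The figure reproduces. The concern is what the contrast estimates, not this calculation.

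**Inputs from the documents**
- Phase II: 15 Intervention 2 and 15 control patients (3.2), so 15 + 15 = 30 of the 60 enrolled.
- Individual randomisation on the day, in permuted blocks (3.4.1, 6.2).
- One room instruction for all arms (6.2).
- Comparator: standard care only (1.2, 11.1).
- Q18 has three rated items, one of them room décor (Appendix B).

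**Not in the documents:** the number of procedure rooms, and the effect of the mural alone.

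**What the contrast estimates.** Let S, M and B be the mean distress change under standard care, mural alone, and mural plus music. The intended effect is B − S. If a fraction p of Phase II controls see the mural, the control mean is (1 − p)S + pM, and

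contrast = B − [(1 − p)S + pM] = (B − S) − p(M − S).

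The departure from the intended effect is therefore p times the mural-alone effect, M − S:

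| Controls who see the mural | p | Departure, in multiples of (M − S) |
|---|---|---|
| 0 of 15 | 0 | 0 |
| 5 of 15 | 0.33 | 0.33 |
| 10 of 15 | 0.67 | 0.67 |
| 15 of 15 | 1.00 | 1.00 |

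At p = 1 the contrast is B − M, music given the mural. This needs no assumption that the two components add. For p between 0 and 1, it assumes that exposed and unexposed controls are otherwise alike.

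**Which row applies.** Read literally, sections 5.1 and 6.2 give the last row: one named room with the decal installed, every patient taken to it, and nothing done differently for controls. The first row needs an arrangement that the text does not describe.

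A power figure would need an assumed share of the effect for the mural, for which the documents give no basis. None is claimed.

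**The case against.** The strongest reply is that this argues from silence. The documents never say there is only one procedure room, and the singular may simply distinguish it from the private consent room. The design schematic is not reproduced in the available text, and section 15.5 mentions a Manual of Procedures that is not in the file. Section 13 says staff are trained to deliver the interventions and follow a common onboarding plan, so some delivery detail sits outside 5.1 and 6.2. The definition of controls as standard care only, and the Appendix B wording that presents the décor change only to Intervention 2 patients, show that arm-specific décor was intended.

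Much of this stands. An unwritten arrangement is possible, so the conclusion is conditional and the range starts at zero. The intention is also clear, but none of these places supplies the step that would carry it out. An arrangement that defines the control condition belongs in the protocol.

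Two further points are fair. The mural's own effect is unknown and could be near zero. A null result from 15 per arm would be weak evidence even with unexposed controls, since the stated power is for an effect size of 1.1. Neither removes the mismatch between the stated question and the contrast that the written procedures produce.

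**Conclusion.** The concern holds, with medium confidence, and should be fixed before Phase II starts. Followed as written, 15 of 15 Phase II controls would see the mural. The Intervention 2 versus Control contrast, which uses 30 of the 60 patients, would then estimate music given the mural and would differ from the stated package effect by the whole mural-alone effect. One of the three Q18 items is directly affected.

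This rests on two conditions: that controls use a room where the mural is visible, and that it stays up throughout Phase II. If some controls are kept from it, the departure shrinks in proportion; if all are, it is zero. Phase I is unaffected provided the mural goes up only after Phase I ends, which the text implies but does not state.

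If Phase II is run with every control exposed, it will contain no mural-free controls, and no analysis of its data could recover the package effect.

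**What to change.** Before Phase II starts, add to sections 5.1 and 6.2 that:

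- the mural is installed only after the last Phase I patient; and
- in Phase II it is on a removable panel, or is covered before each control patient enters the room.

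The existing order in section 6.2 allows this, because the arm is known and the pre-procedure survey is complete before the patient is escorted in. If an arrangement that keeps controls from the mural already exists, write it into the same two sections.

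If none of this is feasible, restate the Phase II hypothesis and contrast as music versus no music with the mural present in both arms, and drop both the décor claim and the between-arm comparison of the Q18 room décor item.

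The first option costs a panel or screen, some room set-up before Phase II patients (the documents give no time for this) and protocol wording. Its drawback is that a screened room may differ slightly from the usual one. Recording an existing arrangement, or taking the fallback, costs wording only. No option needs more patients.

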6.1 Pretreatment Period/Screening

Screening (Day -7 to -1)

- During the week prior to a patient's scheduled procedure, study staff will call patients to remind them of their appointment and determine their interest in participating in the study.
- Based on the scheduling, staff will know if participants meet the eligibility criteria "Prior history of at least 1 (one) BMBA at Jefferson outpatient oncology office within the past 2 (two) years." No other eligibility criteria will be evaluated at this time.
- Information about the consent process will be provided to the patient if desired, but the formal informed consent form will be completely reviewed and signed on the day of the procedure in a private room prior to entering the procedure room.

